7.15. Study End (Day 29)

Assessments should occur within +2 days of target Study Day.

Subjects should be followed to Day 29 (28 days post-initial dose of study drug).

- Women who can become pregnant will take a urine pregnancy test. If the test is positive, the results will be confirmed with a blood pregnancy test.
- Nasopharyngeal or oropharyngeal sample for SARS-CoV-2 testing
- SARS- CoV-2 infection symptom score
- Ordinal Scale for Clinical Improvement assessment
- Adverse event assessment
- Concomitant medication assessment

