12.2. Adverse Event Reporting Period

The AE reporting period for this study is continuous and begins at the time of randomization to study treatment and ends on Study Day 29.

In addition, any known untoward event that occurs subsequent to the AE reporting period that the Investigator assesses as related to the investigational medication should also be reported as an AE.

All AEs (both serious and nonserious) must be followed until resolution or until a stable clinical endpoint is reached. All measures required for AE management and the ultimate outcome of the AE must be recorded in the source documentation and in the eCRF.

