2.2.2 Secondary Efficacy Endpoints

The secondary efficacy endpoints include the following:

- The difference in the proportion of patients with clinically meaningful worsening of COVID-19 within 14 days from the start of experimental therapy, as indicated by an increase of at least 2 points on the Ordinal Scale for Clinical Improvement.
- Ordinal Scale for Clinical Improvement during the study to determine time course of severity and resolution of disease
- SARS-Cov-2 Symptom Score during the study to determine the time course of disease symptoms and resolution of symptoms
- SARS-Cov-2 test result at Day 29
- All-cause mortality rate through Day 29
- Proportion of subjects requiring ICU admission from Day 1 to Day 29
- Number of ICU Days from Day 1 to Day 29
- Proportion of subjects requiring mechanical ventilation from Day 1 to Day 29
- Number of days on mechanical ventilation from Day 1 to Day 29

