4.4 Handling of Dropouts or Missing Data

Except for the time to event endpoints (Table 1), partial end dates of prior and concomitant medications (Section 5.6), and partial onset dates of AEs (Section 7.2.1), all other missing data

will be treated as missing and no method for imputation is planned.

Missing data on the time to event endpoints will have events coded as right censored per the following table:

Table 1 Missing Data Coding for Time to Event Data Analyses

Endpoint	Right Censoring
Time to clinical improvement on Ordinal Scale	Subject who did not meet the criteria for clinical improvement on Ordinal Scale or died at any time during follow-up will be right censored as of the date of last non-missing assessment of Ordinal Scale on or prior to Day 29.
Time to resolution of disease	Subject who did not meet the criteria for the resolution of disease or died at any time during follow-up will be right censored as of the date of last non-missing assessment of Ordinal Scale on or prior to Day 29.
Time to resolution of symptoms	Subject who did not meet the criteria for the resolution of symptoms or died at any time during follow-up will be right censored as of the date of last non-missing assessment of symptoms on or prior to Day 29.
Time to clinical improvement on symptoms	Subject who did not meet the criteria for clinical improvement on symptoms or died at any time during follow-up will be right censored as of the date of last non-missing assessment of symptoms on or prior to Day 29.
Subject Survival	Subjects who are still alive as of the last known follow-up will be right censored as of the date of last subject contact when the subject was known to be alive.

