4.6 Data Derivations and Transformations

The following derivations will be used in this study:

Study Day (Note: There is no day 0 in this study):

- Date of assessment – date of 1st Study Drug administration + 1 for assessments done on or after date of 1st Study Drug administration
- Date of assessment – date of 1st Study Drug administration for assessments done before date of 1st Study Drug administration

Baseline Observation: the last non-missing value prior to 1st Study Drug administration.

Duration:

- Duration in days = end date – start date + 1

- Duration in minutes = end time in minutes – start time in minutes

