Subjects who have died without ICU admission during the study will be counted as requiring ICU admission for the analysis.

Number of ICU Days

The number of ICU days from Day 1 to Day 29 will be calculated based on the ICU admission and discharge dates recorded in the eCRF. The calculated number of ICU days will be compared between treatment groups using 2-sided Student's t-test. The 95% CI and p-value will be presented.

If the Student's t-test normality assumption is found to be clearly violated, a sensitivity analysis will be performed using a non-parametric Wilcoxon rank-sum test. The p-value from the test will be presented.

Subjects who died will be assigned as hospitalized in the ICU for the number of days remaining from the day of death to Day 29 for the analysis. Subjects who are alive and never admitted into the ICU will be included in the analysis with a value of zero ICU days.

Subjects who were at ICU at study completion will be assigned an ICU end date equal to the date of completion for the purpose of deriving number of ICU days.

Subjects requiring mechanical ventilation

Subject data pertaining to mechanical ventilation use will be recorded in the database.

The proportion of subjects who were on mechanical ventilation from Day 1 to Day 29 within each treatment group will be analyzed and compared using the method described above for the analysis of subjects requiring ICU admission.

Subjects who have died without mechanical ventilation during the study will be counted as requiring mechanical ventilation for the analysis.

Number of days on mechanical ventilation

The number of days on mechanical ventilation from Day 1 through Day 29 will be calculated based on the start/stop dates of mechanical ventilation recorded in the eCRF. Number of days on mechanical ventilation will be compared between treatment groups using 2-sided Student's t-test. The 95% CI and p-value will be presented.

If the Student's t-test normality assumption is found to be clearly violated, a sensitivity analysis will be performed using a non-parametric Wilcoxon rank-sum test. The p-value from the test will be presented.

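### Three secondary-endpoint rules in the SAP do not hold to its Day 1 to Day 29 window: survival censoring, stays open at completion, and the day of death in ICU (minor)

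*SAP*

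**What the plan says.** **Survival.** SAP 2.2.2 names the endpoint as "All-cause mortality rate through Day 29". SAP 6.2 analyses it as a binomial proportion and, if judged appropriate, by Kaplan-Meier (KM) with a log-rank test. KM probabilities are read at Days 15 and 29, and quartiles are given where the data allow. Table 1 in SAP 4.4 sets the censoring. Its Ordinal Scale rows read "right censored as of the date of last non-missing assessment of Ordinal Scale on or prior to Day 29", and the two symptom rows have the same limit. The Subject Survival row reads "Subjects who are still alive as of the last known follow-up will be right censored as of the date of last subject contact", with no Day 29 limit.

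**ICU and ventilator days.** SAP 2.2.2 and 6.2 define both over Day 1 to Day 29. For a stay still open at the end, SAP 6.2 says: "Subjects who were at ICU at study completion will be assigned an ICU end date equal to the date of completion". The ventilator rule is parallel. Protocol 7.15 allows the last visit some room: "Assessments should occur within +2 days of target Study Day".

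**Deaths.** In the ICU count, a subject who died is treated as in ICU "for the number of days remaining from the day of death to Day 29". The ventilator count adds only the days that remain up to Day 29 and does not mention the day of death. SAP 4.6 gives the duration rule: "Duration in days = end date – start date + 1".

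**The concern.** An endpoint fixed at Day 29 should use data up to Day 29 and no later.

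- **Survival.** A subject who dies on Day 30 is alive in the binomial analysis but could be an event in the log-rank test reported under the same SAP heading. With few deaths, one such event can move that p-value visibly.
- **Open stays.** The completion-date rule conflicts with the stated window. Two subjects with the same ICU course can differ by up to 2 days only because their last visits fell on different dates.
- **Day of death.** The ICU wording can be coded in two ways, and two endpoints that should be built alike have different rules for deaths.

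Each of these comparisons is reported with a p-value. Left as it stands, the text leaves the choice to whoever programs the analysis.

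**Working it through.** **The window.** Under SAP 4.6, study day = date − first-dose date + 1. A date 28 days after first dose is 28 + 1 = Day 29, which reproduces the correspondence in Protocol 7.15. The inclusive length of Day 1 to Day 29 is 29 − 1 + 1 = 29 days, so 29 is the most that any subject should score.

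**Open stay, start on Day a, completion on Day c.** Days = c − a + 1, with c = 29, 30 or 31.

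| Start | c = 29 | c = 30 | c = 31 |
|---|---|---|---|
| Day 1 | 29 | 30 | 31 |
| Day 2 | 28 | 29 | 30 |
| Day 3 | 27 | 28 | 29 |
| Day 10 | 20 | 21 | 22 |

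The first column is the value limited to Day 29. Totals above 29 need a start on Day 1 or 2, but every start gains 1 or 2 days.

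**Death in ICU on Day d (d ≤ 29), stay from Day a.** Observed days are d − a + 1.

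- Remainder including the day of death: (d − a + 1) + (29 − d + 1) = 31 − a, which is 30 for a = 1. For example, death on Day 15 gives 15 + 15 = 30.
- Remainder excluding it: (d − a + 1) + (29 − d) = 30 − a, which is 29 for a = 1.

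The two readings differ by exactly one day per death in ICU. For a death on Day 30 or 31, 29 − d is −1 or −2; the SAP does not say how to handle this.

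**Effect on an arm mean (assumed rates, 50 per arm).**

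- Day of death counted twice: 1 day × the share of the arm dying in ICU. Shares of 5%, 15% and 25% give 0.05, 0.15 and 0.25 day.
- Open stays with completion on Day 31: 2 days × k/50. For k = 1, 3 and 5 this gives 0.04, 0.12 and 0.20 day.

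**Survival: what cannot change.** A KM estimate at Day 15 or 29 uses only events and risk sets up to that day, so limiting follow-up to Day 29 leaves it as it was. The binomial rate is already through Day 29.

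**Survival: what can change.** Both examples below are assumptions, not forecasts.

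1. There are 50 per arm. One PUL-042 death falls on Day 20, and placebo deaths fall on Days 8, 12, 18 and 25, with a fifth on Day 30. All others are censored on Day 31. KM at Day 29 is 0.98 v 0.92 with or without the limit. The log-rank chi-square is 1.90 (p = 0.168) with the limit and 2.82 (p = 0.093) without it.
2. By Day 29 there are 1 PUL-042 and 5 placebo deaths, with O − E = −2.05 and V = 1.50, so p is about 0.09. Suppose that only 6 subjects are still followed and two PUL-042 subjects then die, with PUL-042 making up 3 of 6 and then 2 of 5 at risk. O − E becomes −2.05 + 0.5 + 0.6 = −0.95 and V becomes 1.50 + 0.25 + 0.24 = 1.99, so p = 0.50.

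Late deaths can therefore move the test in either direction. Neither example crosses the 5% level.

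**The case against.** Much can be said for leaving this alone.

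- **The window is stated.** A reader might infer that the ICU and ventilator rules have no Day 29 cut-off. The documents do not support that: both endpoints name the window and both death rules stop at Day 29. A careful programmer might truncate anyway. What stands is that the completion-date rule contradicts the window and the SAP does not say which prevails.
- **The double count rests on the ICU sentence.** The ventilator wording most naturally gives 29. What stands is the ambiguity in one rule and the mismatch between the two.
- **Table 1 defines only censoring.** That a later death is an event is an inference, and the KM analysis sits under a heading that already says Day 29. The inference is nevertheless the literal reading, since a subject who has died is not among those the row censors.
- **Late follow-up may be scarce.** A reader might infer that a selected group of the sickest subjects stays at risk long after Day 29, because Protocol 12.2 says "All AEs (both serious and nonserious) must be followed until resolution or until a stable clinical endpoint is reached". But Protocol 12 and 12.4 keep COVID-19 symptoms and events out of AE reporting, and no vital-status contact is scheduled after the Study End visit. This weakens example 2. Example 1 needs only the +2-day visit window.
- **Long stays from Day 1 or 2 should be rare.** Entry requires an ordinal score of 4 or less, and subjects needing mechanical ventilation at screening are excluded. This stands, and it is why the effect is small.
- **Ordering of survivors and deaths.** A reader might infer that a cap stops a survivor from scoring worse than a subject who died. It does not. With the cap, a survivor in ICU from Day 5 to Day 29 scores 29 − 5 + 1 = 25. A subject admitted on Day 10 who died on Day 12 scores 3 + 17 = 20. That ordering comes from the admission date.

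**Conclusion.** The point holds as a minor one: three SAP rules are wrong or ambiguous as written, for secondary endpoints only.

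- The missing limit in the survival row can affect only the optional log-rank test and percentiles falling after Day 29.
- The completion-date rule adds 1 or 2 days per affected subject and can give 30 or 31 days in a 29-day window.
- The ICU death rule can add one day per death in ICU and does not match the ventilator rule.

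The shift of about 0.04 to 0.25 day in an arm mean rests on assumed shares of deaths and open stays, and the p-value shifts rest on assumed late deaths. SAP 4.5 describes the study as exploratory and makes no multiplicity adjustment. That limits the consequence further, but it does not make the rules consistent.

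**What to change.** Amend the SAP before unblinding:

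1. **Table 1, Subject Survival.** Censor subjects known to be alive at Day 29 at Day 29, and all other survivors at the last date known alive. State that deaths after Day 29 are not events in this analysis.
2. **ICU and ventilator days, open stays.** Set the end date to the earlier of the completion date and Day 29. Taking the earlier date matters: closing every open stay at Day 29 would impute unobserved days for a subject who leaves the study early while in ICU or ventilated.
3. **ICU and ventilator days, deaths on or before Day 29.** To a stay that runs to the day of death, add 29 minus the day of death, so that this day counts once. Say also how it counts when the subject died outside the ICU or off ventilation. Use identical wording for both endpoints and state a maximum of 29 days. For a death after Day 29, count only the days within the window.

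The cost is a few sentences in SAP 4.4 and 6.2. No new data, visits or protocol procedures are needed.

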4.5 Multiple Comparisons

Because of the exploratory nature of this study, there will be no adjustment for multiple comparisons.

4.6 Data Derivations and Transformations

The following derivations will be used in this study:

Study Day (Note: There is no day 0 in this study):

- Date of assessment – date of 1st Study Drug administration + 1 for assessments done on or after date of 1st Study Drug administration
- Date of assessment – date of 1st Study Drug administration for assessments done before date of 1st Study Drug administration

Baseline Observation: the last non-missing value prior to 1st Study Drug administration.

Duration:

- Duration in days = end date – start date + 1

- Duration in minutes = end time in minutes – start time in minutes

5. STUDY SUBJECTS

5.1 Disposition of Subjects

A table of frequency counts and percentages of all subjects who are randomized, and in each analysis set will be provided. Subject disposition including study completion status and reasons for early termination will be tabulated by treatment group and overall. A by subject listing will be provided.

5.2 Protocol Deviations

Distribution of the types of protocol deviations and the number of subjects that deviate from the protocol will be tabulated for the treatment groups in the ITT set. Protocol deviations will also be tabulated by severity (e.g., minor or major) if appropriate. A listing of all protocol deviations will be provided.

5.3 Demographic Characteristics

Descriptive statistics will be used to summarize the demographic characteristics (age, gender, race, ethnicity, height, weight, and Body Mass Index [BMI]) for the ITT set. A by subject listing will be provided.

5.4 Baseline Characteristics

Baseline characteristics of ITT subjects including confirmation of SARS-CoV-2 infection, pulse oximetry if available, and spirometry results at Screening will be listed and tabulated.

5.5 Medical History

All medical conditions and surgical procedures will be classified by system organ class (SOC) and preferred term (PT) using the Medical Dictionary for Regulatory Activities (MedDRA). The number and percent of subjects with each medical condition and surgical procedure will be presented for each SOC and PT for the ITT set.

5.6 Concomitant Medications and Procedures

All concomitant medications collected will be coded using the World Health Organization (WHO) Drug Dictionary. The number and percent of ITT subjects using concomitant medications will be tabulated by Anatomical, Therapeutic, and Chemical (ATC) level 2 and by preferred name. If the ATC level 2 is missing, the higher ATC level term will be used in the medication summary table and data listing.

A listing of all medications will be provided. The listing will include flags for prior medications.

Prior medications are defined as medications that ended prior to the date of first Study Drug administration. Concomitant medications are defined as medications that started at any time but ended on or after the date of first Study Drug administration, including those that are ongoing at study completion. In the case of a partial end date/time, in order to determine whether a medication is prior or concomitant, the following conservative imputation rule will be used: the unknown

portions of a medication end date will be imputed to the latest possible. The imputed medication end date will then be compared with the date of first Study Drug administration to determine if the medication is prior or concomitant.

Note the imputed end date will only be used to determine whether a medication is prior or concomitant. The actual date reported on the electronic case report forms (eCRFs) will be presented in the listing.

Concomitant procedures will be collected via free text in the eCRF. These data will be presented in a listing.

6. EFFICACY ANALYSES

All efficacy analyses will be carried out using the ITT set. Data on all efficacy endpoints will be listed and tabulated as appropriate.

6.1 Primary Efficacy Endpoint and Analysis

The primary efficacy variable is the clinically meaningful worsening of COVID-19 within 28 days from the start of experimental therapy.

The Ordinal Scale for Clinical Improvement is a 9-point scale that measures disease severity. For this study, an increase of 2 or more points is considered meaningful worsening of disease ([Table 2](#)). This endpoint considers changes in disease severity that are observed at any time over the course of this study.

The Ordinal Scale for Clinical Improvement to be used in this study is derived from a draft scale proposed by the World Health Organization^[1] for clinical improvement as presented below:

Table 2 Ordinal Scale for Clinical Improvement (Derived from draft WHO scale)^[1]

Descriptor	Score
No clinical or virological evidence of infection	0
Infected but no limitation of activities	1
Limitation of activities	2
Hospitalized not requiring oxygen therapy (SpO ₂ > 93% on room air)	3
Oxygen by mask or nasal prongs	4
Non-invasive ventilation or high-flow oxygen	5
Intubation and mechanical ventilation	6
Ventilation + additional organ support- pressors, RRT, ECMO	7
Death	8

The null hypothesis is that there is no difference in proportions of subjects with clinically meaningful worsening of COVID-19 through Day 29 between randomized treatment groups; $H_0: \pi_t - \pi_c = 0$. The alternative hypothesis is that the proportions of subjects with clinically meaningful worsening of COVID-19 through Day 29 are different between the treatment groups; $H_1: \pi_t - \pi_c \neq 0$.

Subjects who had an increase of 2 or more points in Ordinal Scale from the baseline will be treated as meeting the criteria for clinically meaningful worsening of COVID-19. The proportion of subjects who met the criteria within each treatment group will be presented along with a two-sided exact (Clopper-Pearson) 95% confidence interval (CI).

The observed difference in the proportion of subjects meeting the criteria between treatment groups along with the exact unconditional 95% CI for risk difference will be calculated. The null hypothesis will be tested using Fisher's exact method and the p-value will be reported.

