7.2. Subject Selection

7.2.1. Inclusion Criteria

Subjects aged 18 years or older must fulfill all of the following inclusion criteria to be eligible for the study:

1. Subjects must have a positive test for SARS-CoV-2.
2. COVID-19 signs and symptoms such as (fever, cough, shortness of breath or fatigue) with onset within the 7 days prior to Screening and/or within 9 days of the first dose administered on Day 1
3. Subjects should be Ordinal Scale for Clinical Improvement score of 4 or less
4. Subjects receiving oxygen should have pulse oximetry $\geq 93\%$ on 3 liters per minute of oxygen or less delivered by nasal prongs
5. Subjects can be receiving standard of care (SOC) for COVID-19, this includes marketed therapies or therapies with Emergency Use Authorization (EUA) for COVID-19 treatment.
6. Subject's spirometry (FEV₁ and forced vital capacity [FVC]) must be $\geq 70\%$ of predicted value.

7. If female, the subject must be surgically sterile or \geq 1 year postmenopausal. If of child-bearing potential (including being $<$ 1 years postmenopausal) and, if participating in sexual activity that may lead to pregnancy, the subject agrees to use an effective dual method of birth control (acceptable methods include intrauterine device, spermicide, barrier, male partner surgical sterilization, and hormonal contraception) during the study and through 30 days after completion of the study.
8. If female, must not be pregnant, plan to become pregnant, or nurse a child during the study and through 30 days after completion of the study. A pregnancy test must be negative at the Screening Visit, prior to dosing on Day 1.
9. If male, must be surgically sterile or, if not surgically sterile and if participating in sexual activities that may lead to pregnancy, be willing to practice two effective methods of birth control (acceptable methods include barrier, spermicide, or female partner surgical sterilization) during the study and through 30 days after completion of the study.
10. Must have the ability to understand and give informed consent.

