7.11.3. Days 3 and 6 (T₀ +30 minutes [\pm 15 minutes])

- Vital signs
- Spirometry
- Adverse event assessment
- Concomitant medication assessment

7.12. Study Day 10

Assessments should occur \pm 1 day of target Study Day.

The following assessments will be conducted:

- Physical examination
- Vital signs
- SARS- CoV-2 infection symptom score
- Ordinal Scale for Clinical Improvement assessment
- Adverse event assessment
- Concomitant medication assessment

7.13. Study Day 15

Assessments should occur within +1 day of target Study Day.

The following assessments will be conducted:

- Physical examination
- Vital signs
- SARS- CoV-2 infection symptom score
- Ordinal Scale for Clinical Improvement assessment
- Adverse event assessment
- Concomitant medication assessment

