4. GENERAL CONSIDERATIONS FOR DATA ANALYSIS

Unless otherwise specified, continuous variables will be summarized using descriptive statistics

(n, mean, standard deviation, median, minimum, and maximum). Categorical variables will be summarized showing the number and percentage of subjects within each category.

Summary results will be provided for each treatment group. All tabulations will be based on pooled data across centers.

Unscheduled visits will be excluded from the summaries but will be included in the data listings.

All statistical tests will be two-sided and tested at the 5% level of significance.

Analyses will be performed using SAS for Windows statistical software, version 9.4 or higher (SAS, Cary, NC), except where other software may be deemed more appropriate.

CTI will perform all efficacy and safety analyses described in this SAP.

Subject data will be listed, sorted by treatment group and subject number. When applicable, listings will be additionally sorted by visit and assessment date/time.

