4.3 Assessment Windows

Data will be summarized by nominal study visit recorded in the database.

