If the test result for a subject is missing at the end of the study or early discontinuation visit, then the subject will be excluded from the analysis. The proportion of subjects with positive test results within each treatment group will be presented along with a two-sided exact (Clopper-Pearson) 95% CI.

The observed difference in the proportion of subjects with positive test results between treatment groups along with the exact unconditional 95% CI for risk difference will be calculated. The null hypothesis of no difference in proportions of subjects with positive test results between treatment groups will be tested using Fisher's exact method and the p-value will be reported.

Mortality Rate through Day 29

Subject status (Alive/Death) will be recorded in the database. If the vital status of the subject is missing at the end of the study, then the subject will be excluded from the binomial analysis for the mortality rate. The subject will be included in the Kaplan-Meier (KM) analysis with right censoring at the date the subject was last known to be alive.

The mortality rate (proportion of subjects who die) through Day 29 within each treatment group will be analyzed and compared using the method as described in Section 6.1.

If deemed appropriate, an alternative analysis will be performed in which the survival rates will be estimated using the KM method. The KM estimates along with 95% CIs and survival curves will be provided. Based on the KM estimates, the survival probabilities and associated 95% CIs on Days 15 and 29 will be reported; in addition, the 25%, 50% (median), and 75% percentiles of the survival time with associated 95% CIs will be provided, as data permit. The survival rates between treatment groups will be compared using Logrank test and the p-value from Logrank test will be presented.

Subjects requiring ICU admission

Subject data pertaining to ICU admission will be recorded in the database.

The proportion of subjects who are admitted to the ICU from Day 1 to Day 29 within each treatment group will be presented along with a two-sided exact (Clopper-Pearson) 95% confidence interval (CI).

The observed difference in the proportion of subjects requiring ICU admission between treatment groups along with the exact unconditional 95% CI for risk difference will be calculated. The null hypothesis will be tested using Fisher's exact method and the p-value will be reported.

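### The primary derivation in SAP 6.1 can miss worsening that starts and reverses between Days 15 and 29, including mechanical ventilation that a secondary endpoint counts

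*SAP*

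**What the plan says.** SAP 6.1 defines the primary event as a rise of 2 or more points from baseline on the ordinal scale within 28 days, and adds: "This endpoint considers changes in disease severity that are observed at any time over the course of this study". It does not say which records supply the score. SAP 6.2 sends the Day 15 version of the endpoint to the same method.

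Three general rules bear on the derivation. SAP 4: "Unscheduled visits will be excluded from the summaries but will be included in the data listings". SAP 4.3: "Data will be summarized by nominal study visit recorded in the database". SAP 4.4 says that missing data other than its listed exceptions "will be treated as missing and no method for imputation is planned".

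The schedule (Protocol Table 1, SAP Appendix A) places post-baseline scores on Days 3, 6, 10, 15 and 29. Protocol 8.2 gives the score no recall period. For Day 15, Protocol 7.13 states: "Assessments should occur within +1 day of target Study Day". Protocol 7.15 allows 2 days after Day 29.

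The ventilation secondaries in SAP 6.2 cover Day 1 to Day 29, and days on ventilation are "calculated based on the start/stop dates of mechanical ventilation recorded in the eCRF". The mortality secondary uses recorded vital status. On eligibility, Protocol 7.2.1 states: "Subjects should be Ordinal Scale for Clinical Improvement score of 4 or less".

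**The concern.** The endpoint is described as covering the whole of follow-up, but scheduled scoring stops for about half of it. An episode that begins after the Day 15 visit and has fallen below the threshold by the closing visit leaves no scheduled score. The general rules lean towards scheduled nominal visits, and 6.1 does not say whether it overrides them. One programmer could take the worst of all recorded scores and another only the scheduled ones. Both could cite the SAP and report different primary counts.

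The sharpest case is ventilation. It meets the primary definition from any eligible baseline and the database holds its dates, yet the primary can classify the subject as not worsened while a secondary counts the same subject. Adverse event data are no planned back-up, because Protocol 12 and 12.4 keep COVID-19 events out of AE reporting.

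**Working it through.** The plan states no event rate or power for this endpoint, so there is no figure of its own to reproduce.

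**Inputs.** Visit days are from Protocol Table 1. Windows are Days 3, 6 and 10 ±1 (Protocol 7.11, 7.12), Day 15 +1 (7.13) and Day 29 +2 (7.15). The baseline limit of 4 is from Protocol 7.2.1. Scale values (ventilation 6 or 7, death 8) are from SAP Table 2. The 50 per arm is from SAP 9.

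**1. Unscored days** = later visit − earlier visit − 1.
- Day 15 to Day 29 on target: 29 − 15 − 1 = 13.
- Shortest allowed: 29 − 16 − 1 = 12. Longest allowed: 31 − 15 − 1 = 15.
- Largest gap between any earlier visits (Day 9 to Day 16): 16 − 9 − 1 = 6.

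**2. Ventilation always qualifies.** The lowest ventilation score minus the highest eligible baseline is 6 − 4 = 2, which meets the criterion.

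**3. Example.** Take baseline 4, a score of 4 on Day 15, ventilation on Days 17 to 24, and a score of 4 or 5 on Day 29. The largest scheduled rise is 5 − 4 = 1, so the primary is not worsened. The secondary counts the subject as ventilated, for 24 − 17 + 1 = 8 days. What must reverse is the time spent at baseline + 2 or above, not ventilation alone. With baseline 2 the subject must also be off oxygen by the closing visit (3 or less), and with baseline 1 out of hospital (2 or less).

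**4. Onset days on which an episode is missed.** An episode with onset on day s and length L covers days s to s + L − 1. It is missed if no visit falls inside it. For the 13 onset days 16 to 28 (a negative count is zero):
- visits on Days 15 and 29: 14 − L
- fewest missed, visits on Days 16 and 29: 13 − L
- most missed, visits on Days 15 and 31: 16 − L

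| Length at or above threshold | Missed of 13, target days | Missed of 13, across windows |
|---|---|---|
| 5 days | 9 | 8–11 |
| 7 days | 7 | 6–9 |
| 8 days | 6 | 5–8 |
| 10 days | 4 | 3–6 |
| 14 days | 0 | 0–2 |
| 16 days | 0 | 0 |

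For onset on Days 2 to 15, checked over all 162 combinations of allowed visit days (3 × 3 × 3 × 2 × 3), episodes of 7 days or more are never missed and 5-day episodes are missed for 0 to 2 of 14 onset days. The problem therefore lies almost wholly in the last gap.

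**5. Illustration only.** Assume that 10% to 20% of worsening starts on Days 16 to 28 and lasts 5 to 10 days. Loss of all events = late share × miss rate.
- Target days: 10% × 4/13 = 3.1% to 20% × 9/13 = 13.8%.
- Across windows: 10% × 3/13 = 2.3% to 20% × 11/13 = 16.9%.

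**6. Effect on the test, assumed rates.** Exact two-sided Fisher power at 50 per arm is 50.8% for 20% against 5%. If 5% of events are lost in both arms (19.0% against 4.75%), it is 47.5%. If 10% are lost (18.0% against 4.5%), it is 44.0%. One event can also move a result across the 5% level: 1/50 against 8/50 gives p = 0.031, and 1/50 against 7/50 gives p = 0.059.

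**The case against.** The strongest reply is that 6.1 is the specific rule and the general sections yield to it. SAP 4 and 4.3 govern how data are summarized, and an endpoint that counts changes at any time can be read as taking in unscheduled scores. A reader might infer that the SAP orders unscheduled scores out of the primary. It does not say so; it leaves the matter open. But the generous reading still leaves 6.1 without the ventilation dates, so a ventilated subject with no unscheduled score is missed either way.

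It is also fair that the trial is exploratory (SAP 4.5) with no power target (SAP 9), and that the eCRF is not among the documents, so sites may record more than the protocol shows. Both limit what can be said about size. Neither supplies a derivation rule.

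Other stronger inferences fail:
- **Deaths are lost.** Death is 8 and does not reverse. It could be missed only if held solely as vital status.
- **The result is biased towards one arm.** Nothing in the documents shows unequal loss.
- **The 2–17% range is what the fix would recover.** It is assumed, and it covers all late worsening, including milder episodes that dated ventilation and death records do not reach. A reversed rise from 1 to 3 also contradicts none of the ventilation, ICU or mortality secondaries.
- **Missing scores and late withdrawals are further contradictions.** For missing vital status SAP 6.2 says "then the subject will be excluded from the binomial analysis for the mortality rate", while 6.1 leaves its denominator to the general rule in 4.4. Protocol 7.14 ties early-termination assessments to leaving before Day 15 is completed, but 11.2 asks them of all who withdraw. These are details to tidy.

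**Conclusion.** The point stands, and the text should be fixed before unblinding. Followed as written, the plan can classify a true primary event as a non-event although the database holds the dates that prove it and a secondary uses them. That rests only on the visit schedule, the scale and the baseline limit, and needs no assumed rate.

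The size is unknown. The documents give no event rate, share of late onsets or episode length, so the loss and power figures above are illustrations. What the schedule alone shows is that reversed episodes starting on Days 16 to 28 are exposed, and that only those of 16 days or more are always caught, provided both visits take place. The Day 15 endpoint inherits the unclear wording but little of the gap.

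**What to change.** In SAP 6.1, and for the Day 15 endpoint in 6.2:

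1. Derive the event from the worst ordinal score at any scheduled, unscheduled or early-termination assessment after first dose. State that the SAP 4 exclusion of unscheduled visits does not apply to these two endpoints.
2. Count any recorded mechanical ventilation as at least 6 and any death as 8, whether or not a visit took place.
3. Use one fixed calendar cut-off for ventilation, death and unscheduled scores in all subjects: Study Day 29, or Day 15 for the secondary. The Day 29 limit matches the ventilation, ICU and mortality endpoints in SAP 6.2. Assign a closing-visit score taken inside its window to its nominal visit, but do not count an event that starts after the cut-off. Ventilation starting on Day 30 before a Day 31 visit is then outside both primary and secondary, and follow-up does not depend on attendance.

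The cost is SAP wording and minor programming on data already collected, with no extra visits or subjects. The change recovers ventilation, death and unscheduled-score events only. Reversed hospitalization or low-flow oxygen episodes with no unscheduled score stay missed unless an optional eCRF field for the worst score since the last visit is added, which brings some recall error.
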